Effect of Unilateral Ultrasound-Guided Subcostal Transversus Abdominis Plane Block  
in Patients Undergoing Laparoscopic Sleeve Gastrectomy

PI: [name]

NCT03856788

Document Date: Sept 9, 2019

**Title:** Effect of Unilateral Ultrasound-Guided Subcostal Transversus Abdominis Plane Block in Patients Undergoing Laparoscopic Sleeve Gastrectomy

**Researchers:** [name], [name], [name], [name], [name], [name]

**Hypothesis:** Laparoscopic sleeve gastrectomy patients who receive unilateral ultrasound-guided subcostal transversus abdominis plane (TAP) block will have decreased opioid consumption

### **Objectives**

Primary Objective:

Compare amount of intravenous (IV) opioid consumption within 24-hour period amongst laparoscopic sleeve gastrectomy patients who receive the unilateral ultrasound-guided subcostal TAP block with bupivacaine to those who receive the block with only sterile saline.

Secondary Objectives:

- a. Amount of intraoperative IV opioid consumption
- b. Amount of post-operative IV opioid consumption
- c. Severity of pain at rest using an 11-point numeric pain score Likert scale at 1, 6, 12 and 24-hour marks postoperatively
- d. Time to breakthrough pain after surgery
- e. Area of pain after surgery
- f. Presence of postoperative nausea (yes/no) at 1, 6, 12 and 24-hour marks postoperatively
- g. Time to ambulation after surgery
- h. Analgesia satisfaction score at end of hospital stay
- i. Hospital length of stay

### **Background**

Over the last decade, there has been an increasing number of people undergoing bariatric surgeries, including laparoscopic sleeve gastrectomy. While these surgeries are performed laparoscopically, many patients still have considerable amounts of pain. The Enhanced Recovery After Surgery (ERAS) Society recommends a multimodal analgesic strategy for managing pain for laparoscopic sleeve gastrectomy patients so as to improve patient comfort, and minimize opioid consumption, thereby also reducing the complications associated with narcotic use, such as nausea, respiratory depression, and reduced bowel motility. However, there is currently no consensus as to the best pain management strategy for these patients. Several different approaches to effective analgesic management for bariatric patients have been proposed. Studies comparing patient-controlled epidural to standard IV patient-controlled (PCA) opioid analgesia have been promising. However, epidural placement in morbidly obese

individuals may be technically challenging. Furthermore, complications from epidural analgesia including hypotension, dural puncture, and spinal infection or injury can be catastrophic, limiting routine placement in patients undergoing bariatric surgery. Rectus sheath blocks have shown potential to reduce postoperative pain in patients undergoing upper abdominal surgeries, but no studies have evaluated its specific effects in laparoscopic bariatric surgery . Local anesthetic infiltration into trocar sites have also been suggested, but so far has not been shown to reduce postoperative pain .

Recently, transversus abdominis plane (TAP) blocks have garnered attention due to the relative ease of placement and low risk for complications.  The goal of the TAP block is to deposit local anesthesia in the plane between the internal oblique and transversus abdominis muscles so as to anesthetize the anterior rami of the T7-L1 . Studies have found that the classic TAP block, in which the needle enters at the lumbar triangle of Petit, provided analgesia only up to T10, making this block more suitable for lower abdominal surgeries , and less ideal for laparoscopic sleeve gastrectomy. Recent studies are now focusing on modified TAP blocks as a means to provide adequate perioperative analgesia for these patients . Ibrahim et al. compared the effects of bilateral oblique subcostal TAP blocks, local anesthetic infiltration alone at port sites, and no block or infiltration; compared to the other two groups, patients receiving bilateral oblique subcostal TAP blocks had significantly lower pain scores postoperatively for patients undergoing laparoscopic sleeve gastrectomy surgeries . Despite these positive results, oblique subcostal TAP blocks are harder to perform than the standard subcostal TAP block, requiring a longer ultrasound needle and larger volumes of local anesthetic . Ari et al. also did not find any difference in pain scores between patients receiving bilateral subcostal TAP blocks to those receiving both bilateral subcostal and posterior TAP blocks .

Adequate perioperative analgesia is immensely important for bariatric patients, yet there is still no current consensus on optimal pain control. Regional anesthesia techniques are showing promising results. We propose that a unilateral subcostal TAP block, which is easy to perform with minimal risks to patients, may help in minimizing pain and nausea for patients undergoing laparoscopic sleeve gastrectomy.

## **Eligibility Criteria**

### **Inclusion Criteria:**

- Adults 18-80 years old
- Candidate for general anesthesia
- Undergoing laparoscopic sleeve gastrectomy
- Patients of participating surgeons

### **Exclusion Criteria:**

- Prior bariatric surgery of any kind

- Previous abdominoplasty
- Allergy or intolerance to one of the study medications
- ASA  $\geq 4$
- Chronic opioid use (taking opioids for longer than 3 months or daily oral morphine equivalent of  $>5$ mg/day for one month)
- History of alcohol/drug abuse
- History of hepatic or renal insufficiency
- Patient refusal
- Patients who do not speak English

### **Other Aspects that Could Increase Subjects' Vulnerability**

Patients undergoing surgical procedures often have anxiety with surgery. Anesthesiologists will treat this perioperatively with medications and reassurance.

### **Safeguards to Protect Subjects' Rights and Welfare**

Perioperative anxiety will be treated by reassurance and medications as per standard of care. Regardless of participation in the study, patients will undergo their scheduled surgery. Patients will be provided contact information on the consent form in case of any rising concerns or suggestions. Researchers will ensure that protected health information be kept safe and confidential.

### **Duration of Participation**

Individual participation in this study will conclude following discharge from the hospital after laparoscopic gastrectomy surgery. Duration of participation will depend on the length of hospitalization. Typical duration of stay for this type of surgery is usually 1–3 days.

### **Procedures for Subjects to Request Withdrawal**

Patients may withdraw from the study at any point in the investigation. Patients will be provided with contact information and must withdraw in writing. Should this decision be made prior to the procedure, the patient will undergo the surgery as per current standard of care; they will not be included in the experimental protocol. If they choose to withdraw following surgery, post-operative data collection will stop. Regardless of decision to withdraw from the study, subjects will receive current standard of care. Collected PHI will be destroyed at the time of withdrawal.

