### **Procedures for Investigators to Withdraw Subjects**

The patient will be informed if they need to be withdrawn from the study. Should this decision be made prior to the procedure, the patient will undergo the surgery as per current standard of care; they will not be included in the experimental protocol. If this is decided following surgery, post-operative data collection will stop. Regardless, subjects will receive current standard of care. Collected PHI will be destroyed at the time of withdrawal.

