### **Provisions to Protect the Privacy Interests of Subjects**

De-identified data will be stored on secure, password-protected servers maintained by the Mount Sinai Information Technology department. Access to the data will only be available to Mount Sinai IT administrators and the study investigators. A one-way hash ID will be generated for each record once the de-identified data set is released for analysis. Only the study investigators with access to the full data set will be able to match the hash ID to the original record. All investigators must have completed the HIPAA training pertaining to PHI confidentiality.

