### **Description of Study Design**

Patients who are eligible for this subject will be invited to participate. Written informed consent will be obtained from eligible volunteers for this study.

This study will be a double-blinded randomized control trial. Patients will be randomized into one of two groups. Patients in Group 1 will undergo general anesthesia with a post-induction, post-intubation, pre-procedural subcostal TAP block with 40 mL 0.25% bupivacaine on the ipsilateral side as the extraction site. Patients in Group 2 will undergo general anesthesia with a post-induction, post-intubation, pre-procedural subcostal TAP block with 40 mL sterile normal saline on the ipsilateral side as the extraction site. Investigators will be blinded to the randomization of these patients. Following performance of these blocks, patients will receive standard care for the surgery as well as during the postoperative recovery period. Data will be obtained from the EPIC electronic medical record, and from the anesthesia computer record. Patients will be asked postoperatively to assess items such as their nausea and pain scores. Patients will also be contacted by phone within 1-2 days of discharge to obtain analgesic satisfaction scores. This data will be collected on the Redcap server.

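### The withdrawal rules order collected PHI destroyed with no exception for outcomes already recorded, so a completed 24-hour primary outcome can be lost after randomisation and treatment

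*Protocol*

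**What the plan says.** The protocol allows withdrawal at any time: "Patients may withdraw from the study at any point in the investigation". Under *Procedures for Subjects to Request Withdrawal*, two separate things follow when a patient leaves after surgery. Future collection ends: "If they choose to withdraw following surgery, post-operative data collection will stop". Material already in hand is also dealt with: "Collected PHI will be destroyed at the time of withdrawal". *Procedures for Investigators to Withdraw Subjects* closes the same way: "Regardless, subjects will receive current standard of care. Collected PHI will be destroyed at the time of withdrawal". That section gives no criteria for withdrawing a patient after surgery.

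The primary objective has a short window: "Compare amount of intravenous (IV) opioid consumption within 24-hour period amongst laparoscopic sleeve gastrectomy patients". Follow-up in hospital can run beyond it: "Typical duration of stay for this type of surgery is usually 1–3 days".

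On coding of records, *Provisions to Protect the Privacy Interests of Subjects* says: "A one-way hash ID will be generated for each record once the de-identified data set is released for analysis". The same section opens by saying that de-identified data are stored on secure servers.

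The protocol's data analysis section says only who will do the analysis. The SAP lists tests and summary measures. Neither document defines an analysis population, a missing-data method or the handling of withdrawn patients.

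**The concern.** Stopping further collection at withdrawal is ordinary. Removing outcomes already observed is a different matter, because it takes a patient out of the randomised comparison after treatment and after the result exists. If the reason for leaving has anything to do with pain or opioid use, which the block is meant to change, the patients who remain are no longer a fair comparison. Once the research record has gone, the analyst cannot include those patients as randomised, and cannot use their observed values in a sensitivity analysis.

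The investigator rule is the sharper of the two, because it can remove a record without any request from the patient.

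**Working it through.** The documents give no sample size, power, SD or withdrawal rate, so there is no plan figure to reproduce. The check is mainly textual, followed by an illustration on assumed values.

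**1. Does PHI reach the outcomes?**

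- *Description of PHI that will be Shared* names age, sex, BMI and ASA status. None of these is a direct identifier, so the term is not confined to identifiers.
- *Description of Health Information that will be Viewed, Recorded or Generated* lists opioid use, pain, nausea and the other outcomes. Its heading says health information and does not itself use the term PHI.
- *How PHI will be Protected from Improper Use or Disclosure* covers the extracted REDCap data.
- *When and How PHI will be Destroyed* and *Duration Data will be Stored* both describe deletion after publication, the first of PHI and the second of the data.
- The hash ID is tied to release of the data set for analysis. A patient who withdraws during the trial does so before that step.
- Against this, the privacy section also speaks of stored de-identified data, and the PHI protection section mentions the hash ID without giving a time.

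Taken together, the natural reading is that the research record goes, outcomes included. No passage says that coded outcomes survive.

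**2. Can withdrawal follow a complete primary outcome?**

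A stay of 1–3 days is about 24 to 72 hours. Subtracting the 24-hour outcome window leaves 24 − 24 = 0 to 72 − 24 = 48 hours, taking both clocks to start together, which is an approximation. So the exposed interval is close to nil for a one-day stay and up to about two days for a three-day stay. A patient leaving in that interval can have a full opioid total and all four pain and nausea assessments (1, 6, 12 and 24 hours).

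**3. How large could the bias be?**

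Assume that opioid use in one arm is normal and that exactly the top fraction *p* of users in that arm is removed. The mean of those left shifts, in SD units of the full arm, by −φ(z₁₋ₚ)/(1 − p), where φ is the standard normal density:

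| *p* removed | Shift in that arm's mean (SD) |
|---|---|
| 0.02 | −0.049 |
| 0.05 | −0.109 |
| 0.10 | −0.195 |

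Removal from the saline arm understates a benefit; removal from the bupivacaine arm overstates it. For an assumed true difference of 0.5 SD, the 10% case gives 0.5 − 0.195 = 0.305 SD or 0.5 + 0.195 = 0.695 SD.

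**4. What if withdrawal is unrelated to outcome?**

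Assume a two-sided 5% test, 1:1 allocation and about 80% power, with loss at random from both arms:

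| Assumed effect (SD) | n per arm | Power, no loss | 5% lost | 10% lost | 15% lost |
|---|---|---|---|---|---|
| 0.5 | 63 | 0.801 | 0.781 | 0.759 | 0.735 |
| 0.7 | 33 | 0.812 | 0.791 | 0.770 | 0.746 |
| 0.8 | 25 | 0.807 | 0.787 | 0.765 | 0.741 |

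A 10% random loss costs about four percentage points of power. There is no bias in this case.

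**The case against.** The strongest reply is that the rule names PHI and not data. On that view identifiers are destroyed, the stored de-identified values remain, and no outcome is lost. This reading is open, and a reader who takes total erasure as the stated rule goes further than the text. What stands against it is that no sentence keeps the coded outcomes, and the protocol's own use of the term points the other way. Even on the narrower reading, the fate of a randomised patient's primary outcome is left to interpretation.

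Three other inferences are tempting and are not supported:

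- *A patient could withdraw, and be deleted, at the satisfaction call.* The protocol does plan such a call: "Patients will also be contacted by phone within 1-2 days of discharge to obtain analgesic satisfaction scores". But *Duration of Participation* ends participation at discharge, and withdrawal must be in writing. The firm case is the interval from hour 24 to discharge.
- *Nothing at all would remain.* Opioid and timing data originate in EPIC and Compurecord, which the rule does not say are destroyed. The fact of randomisation may also survive in an allocation record. The documents are silent on whether a withdrawn patient's data could be extracted again.
- *Withdrawal will be driven by pain, or investigators will favour an arm.* The block is a single injection in a double-blinded trial, and patients receive standard care whether or not they withdraw, so withdrawing brings no extra analgesia. Blinding prevents knowing selection by arm. It does not prevent selection on observed pain or opioid use, which treatment may influence. The link is possible and not shown.

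Deletion at withdrawal may also be a deliberate privacy commitment. The consent pages are not available here, so any remedy has to give way to what patients were told. The absence of a defined analysis set is a wider gap that this point does not depend on.

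**Conclusion.** The point holds as a weakness that should be corrected. As written, and on the natural reading, both withdrawal rules can remove a complete primary outcome from the research data set for a randomised, treated patient, and nothing in the SAP repairs this.

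The size cannot be estimated, because no withdrawal rate is given and the written-request requirement may keep the number small. The shifts of about 0.05, 0.11 and 0.20 SD are a worst case. They rest on normality, on loss in one arm only, and on loss of exactly the highest users. Similar losses in both arms would largely cancel, and losses unrelated to outcome would cost only precision. The case for change rests less on a large expected bias than on the fact that any bias could not be examined once the records had gone, while the remedy is cheap.

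**What to change.** In both withdrawal sections, replace the destruction sentence with:

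> Direct identifiers are removed at withdrawal; coded data collected up to that point are kept and analysed in the randomised group, unless the patient asks for deletion or the consent terms do not allow retention.

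The same rule, with the same exceptions, should apply when the investigator withdraws the patient. Assign the study code at randomisation instead of at data release, so that a coded record exists whenever withdrawal happens. Report withdrawals by arm, with timing and reason.

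The cost is a short protocol and consent amendment, and coded data of withdrawn patients stay on the server. The change may not cover patients who consented under the destruction rule. For them, and if enrolment is already over, report by arm how many records were destroyed.

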### **Procedures for Investigators to Withdraw Subjects**

The patient will be informed if they need to be withdrawn from the study. Should this decision be made prior to the procedure, the patient will undergo the surgery as per current standard of care; they will not be included in the experimental protocol. If this is decided following surgery, post-operative data collection will stop. Regardless, subjects will receive current standard of care. Collected PHI will be destroyed at the time of withdrawal.

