### **Description of Procedures being Performed**

Group allocation and instructions on preparing the injectate solution for the subcostal TAP block will be included in a sealed envelope. On the day of the surgery, the group allocation will be

revealed to an anesthesiologist not involved with the research study. The anesthesiologist will prepare the solution to be used for the subcostal TAP block.

Standard ASA monitors will be applied to all patients. A preoperative intravenous line will be placed. Patients will undergo standard induction with IV propofol, fentanyl and rocuronium. All study patients will receive 1.5mcg/kg of IV fentanyl on induction. Following induction, a subcostal TAP block will be performed on the ipsilateral site as the extraction site. Patients will be positioned in the supine position. A linear ultrasound probe will be parallel to the lower margin of the rib cage. The rectus abdominis muscle, posterior rectus sheath, and transversus abdominis muscle are identified on the ultrasound. A block needle will be advanced using an in-plane approach from medial to lateral, targeting the fascial plane between the posterior rectus sheath and the transversus abdominis muscle. For group 1 patients, 40mL of 0.25% bupivacaine will be deposited in this fascial plane. For group 2 patients, 40mL of normal sterile saline will be used instead.

General anesthesia will be maintained with inhalational anesthetic gas. Boluses of fentanyl will be given to all patients for pain control as needed, regardless of which group they are assigned to. Patients will also receive muscle relaxants for surgical relaxation as needed. Standard intravenous antiemetics, 8mg ondansetron and 10mg dexamethasone, will be given at the end of the surgery prior to extubation, unless otherwise contraindicated. Surgeons will use local anesthetic to subcutaneously infiltrate the other port sites. Following extubation, patients will recover in the post-anesthesia care unit (PACU) and then to the general hospital floor. Patients will be given scheduled intravenous acetaminophen 1000 mg and ketorolac (30 mg), as well as PRN intravenous opioids, i.e. fentanyl, hydromorphone.

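### Withdrawal is tied to an undefined procedure instead of to allocation, and no analysis set brings back patients removed after the envelope is opened

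*Protocol*

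**What the plan says.** Both withdrawal sections of the protocol have the same two branches.

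- **Early branch.** The patient-initiated rule opens with "Should this decision be made prior to the procedure". The investigator rule reads "Should this decision be made prior to the procedure, the patient will undergo the surgery as per current standard of care", and continues that "they will not be included in the experimental protocol".
- **Late branch.** In the investigator section: "If this is decided following surgery, post-operative data collection will stop". The patient section has the equivalent.
- **Both branches.** Each section closes with "Collected PHI will be destroyed at the time of withdrawal".

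Neither section mentions randomisation or allocation, and neither defines the procedure. The investigator section lists no grounds for withdrawal. The patient section adds a formal requirement: "Patients will be provided with contact information and must withdraw in writing".

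On timing, the Description of Study Design gives Group 1 a "post-induction, post-intubation, pre-procedural subcostal TAP block with 40 mL 0.25% bupivacaine", and Group 2 the same block with saline. The Description of Procedures being Performed puts the allocation in a sealed envelope, revealed on the day of surgery to an anesthesiologist outside the study, after which "The anesthesiologist will prepare the solution to be used for the subcostal TAP block".

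The SAP is one paragraph on descriptive statistics, tests and regression. It names no analysis population and has no rule for withdrawals or missing data.

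**The concern.** Once allocation has been made, a randomised comparison is protected only if every allocated patient is counted in the assigned group. Here the line between not in the study and in the study falls at some point after allocation, and the SAP does not restore anyone lost in between.

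The loss could also differ between the arms. The protocol's Risk to Subjects section names local anesthetic toxicity among the block's complications. Of the two block solutions, only bupivacaine can cause it. A withdrawal prompted by such a reaction would come from one arm only. Blinding limits deliberate selection by investigators, but it does not prevent a removal that the injectate itself triggers.

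**Working it through.** The plan has no figure to reproduce: it states no sample size, effect size, standard deviation or withdrawal rate. The check sets the sections side by side.

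**1. Order of events.** From the Summary of Study Design and the Description of Procedures being Performed: allocation is revealed and the solution prepared on the day of surgery; the block follows induction and intubation; surgery follows the block.

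**2. What procedure means.** For surgery: the Description of Study Design calls the block pre-procedural, How Participants will be Identified attaches the word procedure to the gastrectomy, and the paired branch refers to surgery. For the block or study intervention: How Participants will be Identified also speaks of agreeing to the procedure when describing consent, and the investigator rule uses procedure and surgery as separate terms within one sentence.

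**3. Which rule applies at each stage.**

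| Stage at withdrawal | If procedure = surgery | If procedure = block |
|---|---|---|
| Envelope opened, block not given | Early branch: not included | Early branch: not included |
| Block injected, surgery not begun | Early branch: not included | No rule |
| During surgery | No rule | No rule |
| After surgery | Collection stops | Collection stops |

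The first row is the same under both readings, so removal after allocation is permitted either way. The second row depends on the reading. Under both, part of the day has no rule, and the sentence on destroying PHI applies at whatever point withdrawal occurs.

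**4. Who can trigger it.** A patient must withdraw in writing, which is not possible under anaesthesia. From induction to the end of surgery only the investigator rule can operate, and it has no stated criteria.

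**5. Recording of harms.** The two data lists (Description of Data that Will be Collected Including Long-Term Follow-Up; Description of Health Information that will be Viewed, Recorded or Generated) contain no adverse-event item for any patient.

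**6. Illustrative size.** Assume a share f of blocks is incomplete, equal in both arms and unrelated to prognosis, with no effect in those patients, and an effect D among completed blocks.

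- Effect of assignment = (1 − f) × D + f × 0 = (1 − f) × D
- Ratio of the effect with incomplete blocks dropped to the effect of assignment = D / [(1 − f) × D] = 1 / (1 − f)
- f = 0.05: 1 / 0.95 = 1.053
- f = 0.10: 1 / 0.90 = 1.111

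Both values of f are assumptions. The ratio is the gap between two definitions of the effect. It does not measure the arm-dependent loss, for which the documents give no inputs.

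**The case against.** The strongest reply is that the withdrawal sections govern care and data collection, not analysis. Saying that a patient is outside the experimental protocol does not say that the patient is deleted from the patient flow or the comparison. That is fair: the exclusion is permitted because the SAP is silent, not because the protocol orders it. The silence is why the point stands.

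A reader might infer three stronger things that the documents do not support.

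- **That an injected patient will be treated as never enrolled.** This holds only if procedure means surgery. That reading is the better supported, but the early branch looks forward to surgery under standard care and fits most naturally a patient who has not yet had the injection.
- **That the choice of cut-point causes block harms to be lost.** PHI is destroyed on withdrawal before or after surgery, and adverse events are not listed as study data for anyone. Moving the cut-point alone would cure neither. The documents also do not define PHI as all study data, so de-identified records might survive.
- **That the result would describe only blocks that worked.** No section makes a failed block a ground for withdrawal. The patient is anaesthetised, so analgesic failure would not be apparent from the patient before incision. A plane that cannot be seen is found before injection and, under blinding, should not depend on arm.

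It also stands that the protocol calls block complications rare, so arm-dependent removals may be few. Surgeons infiltrate the other port sites with local anesthetic in both arms, so the toxicity contrast concerns the block solutions only.

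**Conclusion.** The concern holds in limited form. The withdrawal rules use an undefined procedure where they should use allocation, leave part of the operative day without a rule, stop collection after a post-surgery withdrawal, and destroy collected PHI at any withdrawal. With no analysis set in the SAP, an allocated patient can be removed at the investigator's discretion and left out. That is true on either reading of procedure; only the extension to an already injected patient depends on the reading.

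The size is unknown. Under the assumed 5% to 10% of incomplete blocks with no effect, dropping them inflates the apparent effect by about 5% to 11% relative to the effect of assignment. Any toxicity-driven loss would fall on one arm, but its frequency cannot be derived. Nothing in the documents shows that such exclusions occurred. The wording should be corrected; confidence in the point is moderate.

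**What to change.** - **Procedures for Investigators to Withdraw Subjects.** Allow removal without follow-up only before the allocation envelope is opened. After that, an investigator's decision to stop the intervention does not end data collection, and data already collected are kept.
- **Procedures for Subjects to Request Withdrawal.** After the envelope is opened, keep data collected up to withdrawal as far as consent allows, and report the patient in the flow by arm.
- **SAP.** State that the primary analysis includes every patient whose envelope was opened, in the assigned group, whether or not the block was completed, using opioid data from EPIC and Compurecord. Report patients whose operation did not take place, and who therefore have no 24-hour outcome, by arm with the reason.
- **Both protocol data lists.** Add block completion, withdrawal reason and block-related adverse events.

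It is not enough to move the late branch from surgery to envelope opening. The sentence that stops data collection would then apply to every withdrawal after allocation, and the PHI sentence would remain.

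The cost is a few sentences and a few form fields. The opioid data already come from the two named record systems, so no new source is needed. The downside is a slightly smaller apparent effect when incomplete blocks are kept.
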